10.3 Clinical investigation assessments

10.3.1 *Implant/abutment complex capability to provide a reliable anchorage for a sound processor after MONO surgical procedure*

The primary endpoint variable of this study ('capability to provide a reliable anchorage for a sound processor') is a composite variable depending on the outcome of five other variables:

- I. Implant in situ [Implant survival: No/Yes] (see section 10.3.2);
- II. Implant stable [Implant stability: No/Yes] (see section 10.3.3);
- III. Absence of:
 - a. adverse skin reaction (Holgers score ≥ 2) preventing use of sound processor [No/Yes] (see section 10.3.4.2);
 - b. pain preventing use of sound processor on implant/abutment complex [No/Yes] (see section 10.3.6);
 - c. skin overgrowth preventing use of sound processor on the implant/abutment complex [No/Yes] (see section 10.3.4.3)

For this composite endpoint to result in a positive outcome [=Yes], all involved variables need to be answered with [Yes]. If any involved variable is answered with [No], the outcome of the composite variable will be considered a failure [=No]. The rate of subjects (or implant/abutments complexes, if a subject is treated bilaterally) with a positive outcome will be used to calculate point estimates of the proportions with a two-sided 95% confidence interval. These point estimates and corresponding confidence intervals will be used to establish the expected level of implant/abutment complexes that are capable to provide a reliable anchorage (i.e. usage) for a sound processor, at the respective time point.

10.3.2 *Implant survival*

At each follow-up visit, the Investigator will assess whether the implant is still in situ (in place) by means of a [No/Yes] question. The rate of implant survival will be calculated from the number of

implants in situ over the number of implants that were placed. The rate of implant failure will be implicit. The reason for any failure (e.g. spontaneous, trauma etc.) will be documented.

10.3.3 *Implant stability*

Implant stability will be assessed by means of the subjective clinical judgement of the investigator. If the implant is firmly situated in the bone and assumed to be sufficiently osseointegrated when gently manipulating the implant/abutment using the fingers, it is judged stable [Yes]. If the implant is loose, with a lack of osseointegration, the implant is judged not stable [No].

10.3.4 *Skin assessments*

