6.1 Summary of comparable devices/treatment options (state-of-the-art)

The MONO Surgery kit that will be investigated in this study is an accessory to a percutaneous implant. The surgical procedure for the placement of percutaneous BAHS implants has been evolving since the launch and CE marking of the Ponto system in June 2008. The initial method involved extensive removal of subcutaneous soft tissue (known as tissue reduction surgery) in the area of implantation, and since then the surgical technique has become less and less invasive. Today the prevailing surgical methods are the so-called linear incision with tissue preservation and punch only/MIPS (Minimal Invasive Ponto Surgery).

The intended use of the MONO Surgery kit is fulfilled when the implantation results in a percutaneous implant/abutment complex that is capable of holding the sound processor in place. The fulfilment of the MONO Surgery kit intended use (and its indirect patient benefit) is therefore not possible to verify *in vivo* without a connection to the outcomes of the implantation.

In a recent systematic review [15], the literature reporting on the Ponto bone anchored hearing system was reviewed. In total, data from 1,352 patients were included in the review.

Audiological outcomes were discussed in 20 publications. Improvement against the unaided

thresholds was demonstrated. The functional improvement was on average 33.9 dB. The effective gain, or remaining air-bone-gap was on average 6.7 dB. All evaluated data showed aided speech reception thresholds significantly below normal speech level. Five studies reported quality of life using the Glasgow Benefit Inventory, 98% reported an improvement when analysing the score on an individual level.

The data on the implant system confirmed earlier findings and refined the knowledge on complication rates. Major complications (intra- or postoperatively) are very rare, with no life-threatening complications reported in the summarized data. The overall implant survival rate was 98%, with an average follow-up time of 17 months (0.25-60 months). Skin reactions are the most common complication. A Holgers score ≥ 2 generally warrants treatment; typically local treatment for a Holgers score of 2, with the addition of systemic antibiotic treatment for a Holgers score of 3. Across the studies included in the review, reactions classified as Holgers 2 or higher occurred in 5% of visits and 15% of patients.

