8 OBJECTIVES AND ENDPOINTS

8.1 Primary objective

Primary objective	Corresponding primary endpoint/outcome variable(s)	Section
A. To investigate the proportion of Ponto implant/abutment complexes providing a reliable anchorage for a sound processor three months after MONO surgical procedure	1. Composite variable [Yes/No] including: I. Implant/abutment complex in situ II. Implant stability III. Absence of: a. Holgers score ≥ 2 , preventing use of sound processor b. Patient-reported pain preventing use of sound processor c. Skin overgrowth preventing use of sound processor	10.3.1

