10.3.4.3 IPS-scale

The IPS scale [17] is a new, consistent and uniform assessment scale for both percutaneous and transcutaneous implants for bone conduction devices. For percutaneous implants, the IPS-scale is comprising three parts: inflammation, pain, and skin height, with higher scores reflecting more severe complication. It assesses the following characteristics:

1. Inflammation:
 - Skin Integrity (intact = 0/ not intact = 1)
 - Not intact = observation of a blood crust or persistent minimal blood loss at the skin-abutment junction.
 - Erythema (none = 0/ present = 1)
 - Edema (none = 0/ present = 1)
 - Granulation tissue formation (none = 0/ present = 1)
2. Pain:
 - None = 0
 - Present, but no increase during manipulation abutment AND <6 wks present = 1
 - Present, and increase during manipulation abutment AND/OR >6 wks present = 2

CONFIDENTIAL

- Manipulation = tightening (if needed) or tapping on the abutment
- 3. Skin height:
 - Normal = 0
 - Increased, but able to couple sound processor = 1
 - Above rim abutment/unable to couple sound processor =2

The ratings result in a score compiling the ratings of each parameter, i.e. $I_xP_xS_x$.

The IPS-scale offers a standardized treatment advice for each IPS-scale:

- $I_{0-1}P_0S_{0-1}$ = no treatment
- $I_0P_1S_{0-1}$ = no treatment
- $I_1P_1S_{0-1}$ = local topical treatment
- $I_{2-3}P_{0-1}S_{0-1}$ = local topical treatment
- $I_{0-4}P_2S_{0-1}$ = consider addition of systemic treatment for possible peri-implantitis
- $I_{0-4}P_{0-2}S_2/ I_4P_{0-1}S_0$ = consider revision/removal surgery or longer abutment (in combination with antibiotic treatment, depending on I and P-score)

It is not mandatory to follow the treatment advice, but upon analysis of the data from the study, the actual treatment given to the patients will be compared to the treatment advice as a means of evaluating the scale.

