19.4 Non-reportable events

When performing a BAHS surgery, some intra- and post-operative events are more or less likely to occur (i.e. not 'untoward' per se) (see sections 10.2.3 and 10.3.5). Therefore, in this investigation, the following events will be captured in the eCRF on the applicable study visit. To avoid double-reporting, these events will not be recorded in the AE log, unless the investigator judges them to exceed the level of what is to be expected (i.e. 'untoward' per se):

During surgery;

- Drilling into veins
- Drilling into air pockets
- Dura mater exposed

Post-operative complications

- Bleeding or hematoma
- Pain or numbness
- Skin dehiscence
- Erythema
- Edema
- Granulation tissue
- Skin reactions
- Revision surgery

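### The composite has no rule for complexes restored by revision or abutment exchange before a visit, and does not state that implant loss counts as failure at 6 and 12 months

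*Combined protocol and SAP*

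**What the plan says.** Section 10.3.1 builds the composite from five Yes/No variables: in situ, stable, and absence of a skin reaction, pain or overgrowth that prevents sound processor use. The failure rule is "If any involved variable is answered with [No], the outcome of the composite variable will be considered a failure [=No". The resulting proportions and intervals "will be used to establish the expected level of implant/abutment complexes that are capable to provide a reliable anchorage" (meaning usage) "for a sound processor, at the respective time point". No look-back period is given. The pain item (10.3.6) and the overgrowth item (10.3.4.4) are asked in the present tense.

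Section 12.4 adds one rule about earlier events: for the primary endpoint, a subject withdrawn because the implant was lost (extrusion or elective removal) is a failure. Missing data are not imputed. Section 9.4.4 makes implant loss a withdrawal criterion. Section 8.2 repeats the composite at 6 and 12 months without repeating the implant-loss rule.

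The plan foresees interventions that restore function. For the scores that include skin too high to couple the processor, the IPS advice in 10.3.4.3 is to "consider revision/removal surgery or longer abutment". Section 19.4 lists revision surgery among events captured on the visit eCRF, and says "these events will not be recorded in the AE log, unless the investigator judges them to exceed the level of what is to be expected".

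Component I is worded in two ways. Section 8.1, like the synopsis and 8.2, has "I. Implant/abutment complex in situ". Section 10.3.1 has "I. Implant in situ [Implant survival: No/Yes", with a cross-reference to implant survival.

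**The concern.** Sections 6 and 12.1 give the purpose as establishing the level of successful installations with MONO, and 7.2.2 defines the kit's indirect benefit as a fully functional installation. A complex that needed a second procedure to become usable is not plainly a successful installation, yet it can score Yes on all five items if it is usable on the visit day. With no comparator arm, nothing offsets such cases, and the reported proportion is the study's result.

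Two related gaps bear on the same figure. The status of an abutment exchange depends on which wording of component I is applied. At 6 and 12 months, a subject withdrawn for implant loss has no visit, no imputed value and no stated failure rule, so a definite failure could be left out rather than counted.

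Revision surgery can also be absent from the adverse-event tables under 19.4. It could then appear in neither the headline proportion nor the safety summary.

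**Working it through.** **1. The plan's own figure.** Section 12.2 assumes 85% success and a 95% CI 20 points wide, and states 50 patients. With the Wald formula, n = 1.96² × 0.85 × 0.15 / 0.10² = 48.98, so 49; at n = 50 the width is 2 × 1.96 × √(0.1275/50) = 19.8 points. At 95% success the half-width is 1.96 × √(0.0475/50) = 6.0 points. The lower limit is 89.0%, and cutting the upper limit at 100% gives a width of 11.0 points, the plan's 11%. The sample size reproduces and is not at issue; the point is one of definition.

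**2. Three courses before a visit, scored on the text.**

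| Course | At 3 months | At 6 and 12 months |
|---|---|---|
| Became unusable, soft-tissue revision, usable at the visit | Success: all five items Yes (10.3.1) | Success, same reasoning |
| Abutment exchanged, usable at the visit | Success under the 10.3.1 wording of component I; open under the 8.1 wording | Same |
| Implant lost, subject withdrawn (9.4.4) | Failure (12.4) | Not stated; no imputation (12.4) |

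**3. Where it matters most.** Under Table 4 the sound processor may be fitted as late as the 3-month visit, so some complexes have had little or no use by then. The intervals from 3 to 6 and from 6 to 12 months leave more room for a complex to become unusable and be restored between readings. The implant-loss gap exists only at the later times.

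**4. Size of reclassification.** The documents give no rate of rescue, so the number k is an assumption. At n = 50 each complex is 1/50 = 2 points (slightly less if bilateral cases raise the number of complexes). Starting from an assumed 48/50, with exact (Clopper-Pearson) 95% intervals:

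- k = 0: 48/50 = 96.0% (86.3 to 99.5)
- k = 1: 47/50 = 94.0% (83.5 to 98.7)
- k = 3: 45/50 = 90.0% (78.2 to 96.7)

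**5. Size of the denominator gap.** Section 6.1 cites 98% implant survival over an average of 17 months; 2% of 50 is one implant. Assume one loss and two other failures at 12 months. Counting the loss gives 47/50 = 94.0%; dropping it gives 47/49 = 95.9%, a difference of 1.9 points.

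**The case against.** The strongest reply is that a visit-state endpoint is what the plan intends. The objective is anchorage three months after surgery, 9.1 speaks of patients able to use the processor at that time, and 10.3.1 ties the result to the time point. Whether a complex was ever unusable is a different question. This stands, and it is why the visit-state composite should remain primary.

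A reader might infer several stronger things that the documents do not support:

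- *That nothing before the visit counts.* Section 12.4 counts implant loss as failure for the primary endpoint, so a revision that removes the implant does affect it.
- *That a longer abutment is certainly scored as success.* The two wordings of component I leave this open.
- *That earlier skin trouble is hidden.* Section 8.2 has maximum Holgers score and any Holgers score of 2 or more over 0–3 and 0–12 months, the latter including unplanned visits, and Table 4 collects skin, pain and stability at every follow-up. These cover part of the concern, but not prevented use or revision.
- *That the literature figures size the problem.* Section 6.1 reports that "reactions classified as Holgers 2 or higher occurred in 5% of visits and 15% of patients". The 3:1 ratio covers all such reactions, not those preventing use, and says nothing about revision or abutment exchange. It cannot be carried over to a 3-month window.

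On implant loss, 10.3.2 computes survival over implants placed, and 9.4.4 says collected data will be considered as far as possible. A careful analyst might therefore count the loss at 6 and 12 months. The text does not require it, and naming only the primary endpoint in 12.4 invites the opposite reading.

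Finally, 6.2 argues that technique no longer influences anchorage after osseointegration and primary healing. That bears on attributing late failures to MONO, not on how the 6- and 12-month composite should count them.

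**Conclusion.** The point holds as a gap in definition and reporting. On the literal text, a complex restored by soft-tissue revision before a visit can count as reliable anchorage at 3, 6 or 12 months; the status of an abutment exchange is undetermined; and implant loss is not explicitly a failure in the later composite. The visit-state reading rests on the time-point wording, the present-tense items and the absence of any look-back rule, not on an express statement that earlier events are ignored.

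The effect is likely weaker at 3 months than at 6 and 12. Its size is unknown: 2 points per complex at n = 50, with any count of rescued complexes being an assumption. It does not change the sample size or make the primary endpoint invalid. It merits correction because the study has one arm and its result is a single proportion in which a few complexes matter.

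**What to change.** Keep the visit-state composite as primary, and say in 10.3.1 that it is one. Then:

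1. Reconcile component I across the synopsis, 8.1, 8.2 and 10.3.1, so that the scoring of an exchanged abutment is settled.
2. In 12.4, extend the rule that implant loss is a failure to the 6- and 12-month composite.
3. In 12.3 and the SAP, add one supplementary composite at 3, 6 and 12 months, with its 95% CI, that also counts as failure any complex with revision surgery or abutment exchange for a usability problem since surgery. Report the number of each.

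Limiting the supplement to interventions for a usability problem avoids failing complexes whose abutment was changed for another reason. It also leaves brief problems settled without such an intervention as the visit-state composite scores them; counting every one as failure would be a debatable choice of estimand.

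The cost is SAP wording, one derived variable and a second, somewhat less favourable figure. Section 19.4 says revision surgery is captured in the eCRF. Abutment exchange is named neither there nor among the emphasised events in 10.3.5, so the eCRF must be checked for the exchange and its reason, and a field added if it is missing.

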9.4.4 Criteria and procedures for subject withdrawal or lost to follow up

Subjects are free to discontinue participation in the investigation at any time without affecting the medical care of the subject. If a subject withdraws from the clinical investigation, the reason(s) shall be recorded. If such withdrawal is due to problems related to the investigational device safety or performance, the investigator shall ask for the subject's permission to follow his/her status/condition outside the clinical investigation.

Withdrawal criteria:

- Unwillingness to continue participation in the study
- Loss of implant placed during the study (extrusion or elective removal)
- Patients lost to follow-up (following three documented contact attempts)

Subjects withdrawing from the investigation after implantation will not be replaced. Collected data will be considered as far as possible in analyses.

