12 STATISTICAL DESIGN AND ANALYSIS

12.1 Study design and analysis populations

The investigation is a multinational, multicentre, prospective, single-arm investigation to establish the level of successful implant/abutment complex installations using the MONO surgical procedure. Fifty patients will be included to prospectively study the proportion of implant/abutment complexes that are performing as intended (thus capable of providing a reliable anchorage for the sound processor) three months after using the MONO surgical procedure.

Three analysis populations will be defined in the investigation, i.e. safety-, intention-to-treat- (ITT) and per-protocol- (PP) analysis populations. The data used for the safety-population analysis will include relevant safety data from all consenting subjects in the study. The ITT population will include all subjects undergoing surgery in the investigation. The PP population will include treated subjects that do not have any significant protocol deviation.

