12.3 Statistical methods and analytical procedures

Descriptive statistics will be used. The primary endpoint will be presented both as number and percentage, and by point estimates of the proportions combined with a two-sided 95% CI.

For secondary endpoints, the distribution of categorical and dichotomous variables will be presented both as number and percentage, although the composite variable will be presented as for the primary endpoint. Data will be presented for each time separately as well as across visits, where applicable. The distribution of continuous variables will be given as Mean, standard deviation (SD), Median, Minimum and Maximum.

For the safety endpoint, device deficiencies, adverse events and serious adverse events related to the device will be descriptively reported using frequency tables and listings.

All statistical analyses are to be explained in detail in a statistical analysis plan (SAP). Any deviations from the original analysis plan will be described in a CIP amendment, as deemed appropriate.

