12.4 Missing data and special considerations

Missing data will not be imputed. For the primary endpoint, subjects withdrawn from the study due to loss of implant placed during the study (extrusion or elective removal) will be included in the analysis as a treatment failure (i.e. implant/abutment complex not in situ).

In case of any bilaterally implanted patient, implants will be handled as independent from each other for all implant-related variables, since this is considered more clinically relevant. Patient-variables such as patient characteristics and questionnaires will be presented on a patient-level.

No bias nor confounding factors are expected due to the single-arm design.

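### Section 12.4 counts a lost implant as a failure only for the primary endpoint, so as written known failures leave the 6- and 12-month composite

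*Combined protocol and SAP*

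**What the plan says.** **Composite at 6 and 12 months.** Section 8.2 lists it as a secondary endpoint and refers to section 10.3.1 for its definition. There, one negative component makes the whole composite a failure, and estimates are given for each time point.

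Section 12.4 sets the general rule, "Missing data will not be imputed", and one exception: "For the primary endpoint, subjects withdrawn from the study due to loss of implant placed during the study" are analysed as treatment failures. No such rule is written for the later time points.

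Section 9.4.4 lists among its withdrawal criteria "Loss of implant placed during the study (extrusion or elective removal)" and "Patients lost to follow-up (following three documented contact attempts)".

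Three further passages bear on the later composite:
- Section 12.1: the ITT "population will include all subjects undergoing surgery in the investigation". No analysis population is assigned to any endpoint.
- Section 12.3: secondary categorical variables are given as number and percentage, "although the composite variable will be presented as for the primary endpoint". Analysis detail is left to a SAP, and no separate SAP text is in the documents supplied.
- Section 9.4.4: data already collected from withdrawn subjects are to be used where possible.

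**Implant survival.** Section 10.3.2 has the investigator answer a yes/no question at each follow-up visit. It defines the rate as "implants in situ over the number of implants that were placed. The rate of implant failure will be implicit", and it requires a documented reason for any failure.

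**The concern.** A lost implant is the clearest failure that this trial can record. Under 9.4.4 the loss also ends the subject's participation, so the 6- and 12-month forms are never completed. An analyst who applies 12.4 as written finds no later value, is told not to impute one, and has an exception that names only the primary endpoint. The implant then drops out of numerator and denominator alike. The later composite is computed among implants that have not been lost, and it can rise after month 3 with no new success.

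This matters because section 6.2 relies on the 12-month data to confirm longer-term safety and performance. Section 12.5 has the 3-month results compiled first, and section 21 allows them to be published separately. A reader would then compare a 3-month rate and a 12-month rate built on different rules.

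The survival ratio raises a smaller problem in the opposite direction. If failure is whatever remains after dividing by all implants placed, an implant that nobody saw at the visit falls among the failures. Section 9.4.3 allows bilateral surgery. If such a patient is withdrawn after losing one implant, the later status of the other is unknown too.

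**Working it through.** The plan states no expected figure for either endpoint, so the check counts implants under each reading.

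**Inputs**
- Implants placed: 50. Sections 9.4.3 and 12.2 plan 50 patients; one implant each is assumed.
- Losses: 1 as the base case. Section 6.1 reports "The overall implant survival rate was 98%, with an average follow-up time of 17 months", and 0.98 × 50 = 49 in situ.
- Unknown status at the visit (u): not given in the documents. Assumed values of 0 to 5 are shown.

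**1. Composite at 12 months, 1 earlier loss, every implant seen being a success**

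Successes S = 50 − 1 − u.
Loss dropped: S / (50 − 1 − u). Loss kept as a failure: S / (50 − u).

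| u | Loss dropped | Loss kept | Gap, 1/(50 − u) |
|---|---|---|---|
| 0 | 49/49 = 100% | 49/50 = 98.0% | 2.0 points |
| 2 | 47/47 = 100% | 47/48 = 97.9% | 2.1 points |
| 4 | 45/45 = 100% | 45/46 = 97.8% | 2.2 points |

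At u = 4 the exact (Clopper-Pearson) 95% CI is 92.1% to 100% with the loss dropped and 88.5% to 99.9% with it kept.

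If the loss came before month 3 and everyone was seen, the 3-month rate under 12.4 is 49/50 = 98.0%. The 12-month rate with the loss dropped is 49/49 = 100%, although no implant has improved.

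**2. Composite with more losses, assuming 2 other failures and u = 0**

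With L losses, S = 50 − L − 2, and the gap is S/(50 − L) − S/50.

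| L | Loss kept (exact 95% CI) | Loss dropped (exact 95% CI) | Gap |
|---|---|---|---|
| 1 | 47/50 = 94.0% (83.5–98.7) | 47/49 = 95.9% (86.0–99.5) | 1.9 points |
| 2 | 46/50 = 92.0% (80.8–97.8) | 46/48 = 95.8% (85.7–99.5) | 3.8 points |
| 3 | 45/50 = 90.0% (78.2–96.7) | 45/47 = 95.7% (85.5–99.5) | 5.7 points |

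Each loss is therefore worth about 2 points.

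**3. Survival at 12 months, 1 loss**

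Literal ratio: (50 − 1 − u)/50. Known status only: (50 − 1 − u)/(50 − u).

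| u | Literal | Known status |
|---|---|---|
| 0 | 49/50 = 98.0% | 49/50 = 98.0% |
| 1 | 48/50 = 96.0% | 48/49 = 98.0% |
| 2 | 47/50 = 94.0% | 47/48 = 97.9% |
| 5 | 44/50 = 88.0% | 44/45 = 97.8% |

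Each unknown implant costs the literal ratio 1/50 = 2.0 points, as much as a real loss. The row u = 1 also covers a bilateral patient withdrawn after one loss, within 50 implants placed. With none unknown, the two ratios agree.

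**4. Bias of the known-status ratio**

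If the single loss occurs while all 50 implants are still under observation, Kaplan-Meier gives 1 − 1/50 = 98.0% whatever the later dropout. The known-status ratio with 5 unknown is 97.8%, because the earlier loss stays in while implants seen in situ and later unseen leave. The shortfall is 0.2 points.

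**The case against.** The strongest reply is that a lost implant is not missing data. Its in-situ component is known to be negative, section 10.3.1 makes one negative component a failure, and that section speaks of the result at each time point. Section 8.2 sends the later composite to the same definition. The ITT population includes every operated subject, 12.3 presents the later composite in the same way as the primary, and 9.4.4 wants withdrawn subjects' data used. All of this points towards keeping losses in, and that is probably the intention. What it does not do is override 12.4, where the rule is limited to the primary endpoint. The wording in 12.3 concerns presentation (number, percentage, CI), 12.1 assigns no population to an endpoint, and the definition in 10.3.1 needs an answer at the visit, which a withdrawn subject does not give.

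On survival the reply largely succeeds. A reader might infer that 10.3.2 leaves the denominator open, or that the plan has chosen to score missed visits as failures. The documents support neither. The denominator is named as implants placed. Scoring an unseen implant as lost would assign a value to missing data, which 12.4 rules out, and a missed visit supplies no documented reason for failure. The literal ratio also cannot flatter the device. What stands is a conflict of wording between 10.3.2 and 12.4.

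It is also fair to say that the SAP is the natural place for these rules and may contain them, that no dropout rate is given, and that the survival rate reported beside the composite would still show the loss.

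**Conclusion.** The point holds for the later composite. As written, sections 12.4 and 9.4.4 together remove implants known to have failed from the 6- and 12-month composite, an upward bias of about 2 points per loss: 100% instead of 98.0% with 50 implants and 1 loss. For survival there is only a minor inconsistency, worth 2.0 points per implant of unknown status per 50 placed, and nothing if every implant is accounted for.

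The sizes rest on one implant per patient, on the cited 98% survival carrying over to this trial, and on assumed numbers of losses and unknowns. A reader might also infer that the main result or the choice of 50 patients is in doubt. It is not: the loss rule is explicit for the primary endpoint, and the sample size in 12.2 rests on the 3-month rate. Both affected endpoints are secondary and descriptive, so severity is low. If the SAP already carries losses forward, the protocol text only needs to be aligned with it.

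**What to change.** **Section 12.4**, in place of the rule for the primary endpoint alone: *For the composite at 3, 6 and 12 months, an implant lost at or before the visit counts as a failure at that and every later visit; implants of unknown status are not imputed, and their number is reported.*

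**Section 10.3.2**, in place of the ratio and the implicit failure rate: *Only implants documented as lost count as failures. The numbers placed, lost, of unknown status and analysed are reported at each visit.* Survival is then given in one of two ways:
- by Kaplan-Meier, censored at the last visit with the implant confirmed in situ, or
- among implants of known status, with earlier losses kept as failures.

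The SAP should repeat whichever is chosen, before the 3-month data are analysed.

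**Cost.** Two short text changes and one line of counts per visit, with no extra visits or patients. Kaplan-Meier also needs the date of loss. Later composite rates may come out slightly lower than observed-case rates. The known-status ratio is biased slightly downward (0.2 points in the example with 5 unknown), and the same effect applies to the composite when implants of unknown status are left out. Both survival options assume that unseen implants fare like those still followed, which is why the number unknown must be shown.
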